H_1 = PRO-231 ophthalmic solution does not have a similar safety and tolerability profile as VIGAMOXI® in clinically healthy subjects.

$$H_1: ST_A \neq ST_B \text{ o } ST_A - ST_B \neq 0$$

Operational definition of similarity: To reject H_0 , the p-value in the primary variables must be ≤ 0.05 and the 95% CI of this difference must not include zero. Both conditions for hypothesis testing (p-value and 95% CI) must be met, otherwise the result will be interpreted as "**absence of evidence**", not "**evidence of absence**".

Study Design: Phase I clinical study, controlled, comparative, parallel-group, single-blind, single-center.
Number of subjects (planned and analyzed): Number of planned subjects: 38 (19 subjects per arm).
Diagnosis and main inclusion criteria: Ophthalmologically and clinically healthy subjects.
Selection criteria: Inclusion criteria: 
– Have the ability to voluntarily give their signed informed consent.– Ophthalmologically and clinically healthy subjects.– Be able and willing to comply with scheduled visits, treatment plan, and other study procedures.– Age 18 to 45 years.– Both sexes.– Women of childbearing potential must ensure the continuation (initiated \geq 30 days prior to signing the informed consent form [ICF]) of the use of a hormonal contraceptive method or intrauterine device (IUD) during the study period.– AVMC of 20/30 or better in both eyes.– Corneal staining \leq grade I on the Oxford Scale.– Have an intraocular pressure \geq 10 and \leq 21 mmHg. Exclusion criteria: 
– History of hypersensitivity to fluoroquinolones or any of the components of the PI.– Be a user of topical ophthalmic medications of any pharmacological group.– Be a user of medicines by any other means of administration.– History of eye surgery in the last 6 months.– Wearing contact lenses for less than two weeks prior to the start of the study, and during the study intervention period.– For women: being pregnant, breastfeeding, or planning to become pregnant within the study period.– Have participated in any investigational clinical study 30 days prior to inclusion in this study.– Have previously participated in this same study.– History of any chronic-degenerative disease, including Diabetes Mellitus or Systemic Arterial Hypertension.– Known diagnosis of liver or heart disease.– Have active inflammatory or infectious disease at the time of study entry.

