- Incidence of conjunctival hyperemia and chemosis. (TE: day 3 and 8)
- Changes in the AVMC evaluated with the Snellen chart. (TE: day 3 and 8)
- Changes in ocular surface integrity using fluorescein staining, using the Oxford scale. (TE: day 3 and 8).

Tolerability

- ICO score changes. (TEE: day 8)

Secondary outcome variables:***Safety:***

- Incidence of expected and intervention-related AEs (excluding conjunctival hyperemia and/or chemosis). (TE: day 3, 8 and 12)

[figure not shown]
Tolerability:

- Presence of eye symptoms (burning, foreign body sensation, pruritus and tearing). (TE: day 3 and 8)

Statistical methodology

The analysis of the data collected in the study will be carried out by means of specialized statistical software (SPSS available version or R software). The data will be expressed with measures of central tendency: mean, standard deviation and/or ranges for quantitative variables, and frequencies and/or percentages for qualitative variables. The Shapiro-Wilk test (S-W) will be used to determine if the distribution is normal in the data obtained in each study group ($p>0.05$). If the normality in the distribution of the data is verified, to rule out differences between groups, the Student's t-statistic will be used for independent groups, while intragroup differences will be analyzed with the Student's t-test for repeated measures. In case of $p<0.05$ in S-W, the statistical analysis to rule out differences between groups will be performed by means of the Mann-Whitney U test for quantitative variables, while intragroup differences will be performed by Wilcoxon's rank test. The difference between the qualitative variables will be analyzed by means of the χ^2 statistic (Chi-squared) or Fisher's exact (for expected values less than 5). Dichotomous variables will be analyzed by the McNemar test when applicable. An alpha (α) ≤ 0.05 will be considered as statistical significance, in addition to this, the 95% CI will be calculated for these differences. For primary outcome variables, H_0 will be rejected, when $p \leq 0.05$ and the 95% CI does not include zero.

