7.4.3 Definition of variables, methods and scales for their measurement

Board 2. Operational definition of variables

Variable	Conceptual Definition	Operational Definition	Measurement Type	Reference value	Statistical test
Incidence of Intervention-Related Unexpected AEs	Any adverse medical event that occurs in the clinical research subject to whom any of the interventions were administered and that has a certain coincidental relationship to the interventions [33]	All AEs (according to protocol) in which the PI suspects a causal relationship with the interventions will be reported	• Discrete quantitative • Nominal qualitative	• Relationship with IP • Severity • Causality	
 • Student's t-test of independent groups • U de Mann Whitney* • Pearson X² or Fisher Exact*
Incidence of conjunctival hyperemia	It is the reaction of the conjunctiva to a stimulus, a red appearance secondary to the vasodilation of the conjunctiva vessels of variable intensity is seen	Direct observation. Classification by Efron scale. See attachment 16.2. Efron Scale for Conjunctival Hyperemia	Degrees: 0 = Normal, I = Muy live, II = Mild, III = Moderate and IV = Severe		
 • Pearson X² or Fisher Exact* • McNemar Test*
Incidence of Chemosis	It is defined as conjunctival edema, the result of an inflammatory reaction. It is classified as present or absent	The evaluator will use a narrow beam of light at 60° and will measure whether the conjunctiva separates ≥ 1/3 of the total	• Nominal qualitative	Present / Absent	
 • Pearson X² or Fisher Exact* • McNemar Test*

Variable	Conceptual Definition	Operational Definition	Measurement Type	Reference value	Statistical test
Changes in the AVMC	Visual spatial acuity is the ability to distinguish separate elements of an object and identify them as a whole. It is quantified as the minimum angle of separation (located at the nodal point of the eye) between two objects that allows them to be perceived as separate objects	eyelid opening or if it exceeds the gray line Cartilla de Snellen. Ver anexo 16.5 Fraction to LogMAR conversion table.	• Continuous quantitative	20/30 (0.2 LogMAR) or better	
 • Student's t-test of independent groups • U de Mann Whitney*

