10.3 Statistical methodology

The statistical analysis plan (PAE) was developed considering the evaluation criteria described in the study protocol.

The statistical analysis will be carried out by personnel of Laboratorios Sophia, S.A. de C.V. Specialized statistical software (SPSS version available [IBM Corporation, Armonk, NY, USA] or R [*The R Foundation for Statistical Computing*; <http://www.R-project.org>]), for Windows. The coding will be done using consecutive numbers. The data will be collected and sorted in an Excel spreadsheet (Microsoft® Office). The data will then be exported to the platform of the selected statistical package. The variables will be categorized according to their nature (see [Board 2](#)). The statistical tests used will be following the corresponding assumptions for parametric statistics as long as the assumption of normality is met (Shapiro-Wilk, $p>0.05$).

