10.3.1 Population Analysis

The statistical analysis will be presented to give a general summary of the subjects entered into the study and a view of the safety and tolerability of its results. The data provided by the research site will be summarized for this purpose, according to its nature. The Shapiro-Wilk test will be performed to find out if the quantitative data are distributed in a normal way ($p>0.05$).

The results of the quantitative variables will be presented in measures of central tendency: mean, standard deviation and/or ranges. Changes in the AVMC and ICO will be expressed as continuous variables. Whereas, the incidence (number) of AEs will be expressed as a discrete variable.

The result of the nominal and ordinal qualitative variables will be presented in frequencies, proportions and/or percentages. For these, tables of frequencies $p \times q$ will be constructed. All percentages will be presented with a decimal.

The level of difference to consider significance will be an alpha (α) of 0.05 or less, the 95% CI will be calculated for these differences. The triangulation between the type of variable and the measurements is shown in Table 5. [63]

The operational definition of the study for hypothesis testing will be as follows:

Hypothesis testing	value	Result	Interpretation
P value	≤ 0.05		
95% CI	Does not include zero	H_0 rejected	Both treatments are different in terms of safety and tolerability
P value	≥ 0.05	H_0 accepted	Both treatments are similar in terms of safety and tolerability (they are not different)
95% CI	Includes zero		

Both conditions for hypothesis testing (p-value and 95% CI) must be met, otherwise the result will be interpreted as "**absence of evidence**", not as "**evidence of absence**".

Board 5. Triangulation of concepts.

Variable Type	Variable	A1	A2	B1	C1	C2	C3	C4	D1	E1	F1	F2	F3	F4
Selection														
A1	Demographic			D										
A2	Medical History/Selection Criteria				D									
Basal														
B1	Comprehensive ophthalmological evaluation			T	D	TB	TB	B	T		TB			
Primary Security														
C1	Incidence of unexpected-related AEs				TB					TB				
C2	Incidence of conjunctival hyperemia and chemosis			T		TB				TB				
C3	AVMC			B	TB			B		TB				
C4	Corneal and conjunctival stains with fluorescein			B	TB			B		TB				
Primary Tolerability														
D1	ICO								B					
Secondary Security														
E1	Incidence of AE*			T			TB							
Secondary Tolerability														

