10.3.2 Safety and tolerability analysis

10.3.2.1 Analysis for Primary Variables

The analysis of the primary outcome variables of safety and tolerability will be carried out in the per-protocol population (PP), defined as any subject with an adherence $\geq 80\%$ determined by the subject's diary and corroborated by the final weight of the research product to which it was assigned (PRO-231 or VIGAMOXI)[®] with respect to its initial weight. and that they conclude their participation without deviations from the study protocol.

The Shapiro-Wilk test (S-W) will be used to determine if the distribution is normal in the data obtained in each study group ($p>0.05$). If the normality in the distribution of the data is verified, to rule out differences between groups, the Student's t-statistic will be used for independent groups, while intragroup differences will be analyzed with the Student's t-test for repeated measures.

In case of $p < 0.05$ in S-W, the statistical analysis to rule out differences between groups will be performed by means of the Mann-Whitney U test for quantitative variables, while intragroup differences will be performed by Wilcoxon's rank test.

For qualitative variables, Pearson's X² (Chi-square) or Fisher's exact test will be used in expected values less than 5. Dichotomous variables will be analyzed by the McNemar test when applicable.

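### ICO change is compared with no baseline covariate, and the Mann-Whitney branch for ICO and BCVA change names no effect measure or CI method, although the decision rule needs a CI

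*Combined protocol and SAP*

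**What the plan says.** ICO change is the single primary tolerability variable (section 7.4.1.2). The questionnaire is completed at the baseline and final visits (7.4.4.7). BCVA (AVMC) change is a primary safety variable, assessed at days 3 and 8 (Synopsis). Table 2 lists only the independent-groups t-test or Mann-Whitney for both. On scale, section 10.3.1 says "Changes in the AVMC and ICO will be expressed as continuous variables".

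The choice of test is gated. Section 10.3 allows parametric tests "as long as the assumption of normality is met". Section 10.3.2.1 applies Shapiro-Wilk to "determine if the distribution is normal in the data obtained in each study group", and if it fails, "the statistical analysis to rule out differences between groups will be performed by means of the Mann-Whitney U test for quantitative variables". No model with baseline as a covariate appears anywhere.

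The decision rule has two parts. To reject the null hypothesis, the p-value must be at most 0.05 and "the 95% CI of this difference must not include zero" (Synopsis; same rule in 3.2). Section 10.3.1 adds "Both conditions for hypothesis testing (p-value and 95% CI) must be met"; a mismatch is read as absence of evidence. A CI is promised in general terms: "in addition to this, the 95% CI will be calculated for these differences". Which difference it refers to, and how it is computed when Mann-Whitney is used, is not said.

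For BCVA, the operational definition in Table 2 is "Cartilla de Snellen. Ver anexo 16.5 Fraction to LogMAR conversion table". Acuity is recorded as the smallest line read (7.4.4.4), and the table in 16.5 moves in steps of 0.1 logMAR.

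**The concern.** There are two separate issues.

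**Precision.** The change score gives baseline ICO a fixed coefficient of one. ANCOVA estimates that coefficient and usually yields a narrower interval from the same data. At 17 per arm this matters, because the trial was not sized on ICO.

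**An incomplete decision rule.** On the t-test branch, the p-value and the mean-difference CI agree by construction. On the Mann-Whitney branch they need not: the test works on ranks and the natural default interval is for a difference in means. Because the plan makes agreement a decision criterion, an unnamed CI method can decide whether a primary variable gets a definite verdict, and the method would be picked after the data exist. BCVA change is exposed most often, since whole-line readings give heavily tied data that will usually fail Shapiro-Wilk.

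**Working it through.** **Inputs.** The plan gives 17 per arm before losses (10.1.2). It gives no SD, correlation or distribution for ICO or BCVA, so those are assumed below. The 17 comes from adverse-event proportions. With 6/62 against 0.50, unpooled variance, two-sided 0.05 and an assumed 80% power: (0.0874 + 0.25) × (2.802/0.4032)² ≈ 16.3, rounded up to 17. ICO plays no part in it. At 17 per arm the 95% CI half-width for ICO change is 2.037 × √(2/17) = 0.70 SD of the change.

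**Step 1: precision.** Let r be the baseline to day-8 correlation and k the baseline SD divided by the day-8 SD. In units of the day-8 variance:

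- change score: 1 + k² − 2rk
- ANCOVA: 1 − r²

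The CI-width ratio is √[(1 − r²)/(1 + k² − 2rk) × 1.033] × 1.0013. The factor 1.033 (1 + 1/30) allows for chance baseline imbalance with 34 subjects; 1.0013 is the ratio of t quantiles on 31 and 32 degrees of freedom.

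| k | r = 0.3 | r = 0.5 | r = 0.7 | r = 0.9 |
|---|---|---|---|---|
| 1, variance ratio | 0.650 | 0.750 | 0.850 | 0.950 |
| 1, CI width ratio | 0.821 | 0.881 | 0.938 | 0.992 |
| 0.7, variance ratio | 0.850 | 0.949 | 1.000 | 0.826 |
| 0.7, CI width ratio | 0.939 | 0.992 | 1.018 | 0.925 |
| 0.5, variance ratio | 0.958 | 1.000 | 0.927 | 0.543 |
| 0.5, CI width ratio | 0.996 | 1.018 | 0.980 | 0.750 |

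With k = 1 the ANCOVA interval is 1–18% narrower. Over the whole grid it runs from 2% wider to 25% narrower.

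**Step 2: agreement of p and CI.** Simulated trials at 17 per arm take Mann-Whitney when either arm fails Shapiro-Wilk, which is the natural reading of 10.3.2.1. A conflict is a Mann-Whitney p and a mean-difference 95% CI that point different ways.

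- ICO, floor-limited (normal latent score, mean 0–10, SD 10, clipped at zero), or lognormal (median 6–10, log-SD 0.8); r = 0.3–0.7.
- BCVA change in 0.1 logMAR steps, with 50–80% of changes equal to zero.

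| Setting | Conflict |
|---|---|
| No true difference, ICO or BCVA | about 0.3–4% |
| ICO floor-limited, 8-point shift | 1–7% |
| ICO lognormal, 6-point shift | 10–20% |
| BCVA, 30–50% of one arm a line worse | 3–9% |

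In the lognormal setting nearly all conflicts are a significant Mann-Whitney p with a CI that includes zero. For BCVA the gate selects Mann-Whitney in about 95–100% of trials.

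**Step 3: what a conflict does.** The table in 10.3.1 needs both parts for either definite verdict, so a conflict goes to absence of evidence.

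**The case against.** The case for leaving the plan alone has several parts.

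- *The comparison is sound.* This stands. A reader might infer from the missing covariate that the ICO comparison is biased. It is not: baseline is subtracted and allocation is randomised 1:1.
- *The gate does no harm to type I error.* This stands too. A reader might expect test selection to inflate it, but in simulation the gated test stayed at 4–5%.
- *A mean-difference CI is implied*, because mean and SD are the named summaries. It is a plausible default, but those summaries are descriptive, and this is the very interval that can contradict Mann-Whitney.
- *Conflicts matter only with real differences.* Largely true. The higher rates need shifts that no document supports; section 10.1.2 expects similar adverse-event incidence.
- *Discordance is already provided for.* True, and it limits the harm to an inconclusive result.
- *The analyst is blinded* (4.2, 7.3). This reduces the risk of a favourable choice of CI but does not replace specifying it.
- *Lognormal ICO is a harsh assumption*, given the Rasch interval scale described in 7.4.4.7. That is fair; the floor-limited figures may be nearer.
- *ANCOVA is not always better.* Correct. With lognormal scores (median 8), its power is 54% against 57% for the gated p alone at r = 0.5, and 67% against 76% at r = 0.7.

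**Conclusion.** The point holds as two modest specification gaps that should be closed before analysis.

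For ICO, the cost of omitting the covariate is precision: 1–18% in CI width with equal SDs, and between a 2% loss and a 25% gain from ANCOVA over the wider range. For ICO and BCVA, the decision rule cannot be applied as written on the Mann-Whitney branch, because the difference and its CI are undefined. The practical risk is an avoidable inconclusive result: rare with no true difference, at most about 20% in the most skewed ICO setting.

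Two stronger readings are not supported. A reader might infer that the gap lets the trial declare similarity wrongly; a conflict cannot do that under 10.3.1. (Reading p of 0.05 or more as similarity is a separate weakness, which this fix does not cure.) A reader might also test a Hodges-Lehmann CI on BCVA, find conflict in 14–61% of shifted trials, and attribute that to the plan. The plan never mentions that interval; the figure is only a reason not to adopt it.

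Confidence is medium. The textual gap is certain; every magnitude depends on assumed distributions and correlations.

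**What to change.** **ICO.** Replace the gated test with ANCOVA of day-8 ICO on arm and baseline ICO. State that the adjusted mean difference, with its p-value and 95% CI, is what enters the decision rule. Add rank ANCOVA as one pre-specified sensitivity analysis.

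**BCVA change, days 3 and 8.** Name one effect measure and take p and CI from the same method, one that tolerates ties. Options are the mean difference with its t-based p and CI, or P(Y>X) − P(Y<X) with the Brunner-Munzel p and CI, whose type I error was 5.2–6.0% at 17 per arm under the assumed distributions. Do not pair Mann-Whitney with a Hodges-Lehmann CI: under heavy ties its endpoint lands on zero.

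State in advance what is reported if no subject changes, or none in one arm. With 80% zero changes, at least one arm shows no change in 1 − (1 − 0.8¹⁷)² ≈ 4% of trials; with 90%, in about 31%.

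**Where.** Eight places: both Synopsis statements (definition of similarity, statistical methodology), 3.2, the AVMC and ICO rows of Table 2, 10.3, 10.3.1 and 10.3.2.1.

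**Cost.** A wording amendment through the committees and COFEPRIS (11.2), with no new data, and one residual degree of freedom. If ICO proves strongly skewed, linear ANCOVA has less power than the gated p alone, and a sensitivity analysis outside the rule does not recover it. Against the full two-part rule with a mean-difference CI, the same lognormal cases favour ANCOVA: 54% against 41%, and 67% against 56%. Part of that gap arises because the two-part rule is conservative (type I error 2.9–4.6%, against 3.7–5.3% for ANCOVA).

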10.3.2.2 Analysis for secondary variables

The analysis of the secondary outcome variables of safety and tolerability will be carried out in the safety population, defined as any subject who has received at least one dose of the investigational product (PRO-231 or VIGAMOXI)[®] regardless of their adherence to it or adherence to the protocol (intention-to-treat population, ITT).

For the analysis of these variables, the same primary analysis will be carried out as long as they have the necessary measurements to do so.

10.4 Other analyses

The final report of the results will be shown in tables or graphs, as appropriate.

10.4.1 Procedure for handling missing data

There is no imputation procedure for missing data.

11. Ethical considerations

11.1 Approval of the committees

The present study will be conducted in accordance with the principles of the Declaration of Helsinki, World Medical Association 2013. Nuremberg Code; Nuremberg Trial by the International Tribunal of Nuremberg, 1947. Belmont Report, National Commission for the Protection of Biomedical and Behavioral Research Subjects, 1979. It will be conducted in accordance with the scientific and technical requirements necessary for the registration of medicines for human use by the International Council for Harmonisation (ICH) Guide to Good Clinical Practice. Council for International Organizations of Medical Sciences (CIOMS, 2002) International Ethical Guidelines for Biomedical Research in Human Subjects. Council for International Organizations of Medical Sciences (CIOMS, 2008) International Ethical Guidelines for Epidemiological Studies. The Research Ethics Committee and the Research Committee will evaluate the protocol before conducting the study and will issue their approval or possible modifications for its performance, these Committees must be notified of any significant changes to the protocol. In addition to the above, the current regulations of the regulatory authority will also be complied with.

The personnel authorized by the sponsor will submit to evaluation by the Research Ethics Committees, Research Committees, and when applicable to the Biosafety Committee the essential documentation of the research project: research protocol, informed consent form, researcher's manual, subject material, as well as other documents additionally requested, according to local requirements, applicable by the regulatory authorities.

The study will not begin at the research center if there are no confidentiality agreements and economic proposal from each of the principal investigators, duly signed and without having previously obtained the favorable opinion and/or approval of the Research Ethics Committees, Research Committees, and when applicable by the Biosafety Committee. Corresponding.

The study will not begin without having complied with the relevant local, national or international regulatory requirements and without having the corresponding health authorization.

The study is considered to be a study with a greater than minimum risk, in accordance with the Regulations of the General Health Law on Health Research, Title Two, Chapter I, Article 17, Section III, published in the Official Gazette of January 6, 1987.

